The predictive utility of intratumoral DRD5 expression will be evaluated in archival tumor specimens based on an inverse correlation with ONC201 efficacy in cancer cell lines. Among the 15 available archival tumor tissue specimens in Arm A, all had expression of DRD2 and 8/17 patients had low expression of DRD5. Patients with PFS > 5 months had no detectable expression of DRD5 unlike those with PFS < 5 months. In addition, 4/8 DRD2+DRD5- and 0/7 DRD2+DRD5+ patients were still alive with a median follow-up of 47.4 weeks. Based on these findings, DRD2+DRD5- patients are expected to have improved PFS and OS in response to ONC201 administration. For Arm B and Arm C, %DRD2 and %DRD5 positive cells (strong/total) will be quantified using image analysis algorithms for detection of DRD2 and DRD5 immunolabeling area and intensity (Visiopharm VIS software). Arms B and C will be combined for these analyses. Patients with pathologist-verified DRD5 staining area in the biopsy of >0.018% strong positive or >1% total positive will be classified as DRD5+. DRD5+ versus DRD5- patients will be compared for key clinical outcomes using a likelihood

ratio chi-square test (ORR) or log-rank test (PFS, OS). Significance will be declared if the two-sided p-value is <0.05 , with no adjustments for multiple comparisons. Because the assay for quantifying the %DRD5 strong positive cells or %DRD5 total positive cells is still being developed to be more precise, the data will also be normalized into Z-scores as a second and independent method of identifying patients as DRD5-positive or negative. Patients with negative Z-scores will be grouped into the DRD5- cohort and patients with positive Z-scores will be grouped into the DRD5+ cohort. The same comparisons for clinical outcome will be performed as above.

Pharmacodynamic effects will be evaluated by assessment of tissue biomarkers based on mechanism of action and preclinical tumor cell sensitivity studies. IHC ATF4, CHOP, and DR5 will be summarized using descriptive statistics.

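### The Z-score split of DRD5 is not independent of the fixed cut-off: it re-cuts the same measurements and adds a second, correlated, unadjusted chance of a significant result

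*Protocol*

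**What the plan says.** Protocol section 13.1 pools Arms B and C for this analysis. A patient is DRD5-positive if more than 0.018% of the staining area is strong positive or more than 1% is total positive. The two groups are compared on ORR by a likelihood ratio chi-square test and on PFS and OS by log-rank tests. The decision rule is explicit: "Significance will be declared if the two-sided p-value is <0.05", "with no adjustments for multiple comparisons".

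The paragraph then says that the assay is still being made more precise and that, for this reason, the same data are also turned into Z-scores "as a second and independent method of identifying patients as DRD5-positive or negative". The rule is that "Patients with negative Z-scores will be grouped into the DRD5- cohort and patients with positive Z-scores will be grouped into the DRD5+ cohort". It ends: "The same comparisons for clinical outcome will be performed as above".

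Three things are not stated:
- the reference mean and SD for the Z-score;
- whether the strong or the total percentage is normalised;
- which classification takes precedence when the two disagree.

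SAP section 3 gives a complete list of outputs with no DRD5 analysis on it. It adds that other protocol analyses will not be completed or will be defined elsewhere.

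**The concern.** Two methods are independent in a useful sense if their errors are separate, for example a second assay, a second reader or a second set of patients. Here the second method is the first measurement with a constant subtracted and the result divided by another constant. It carries the same staining error, in the same patients, against the same outcomes. The procedure described cannot have the property the text claims for it, and it does nothing about imprecision.

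The second split does move the cut point. Some patients change group, the three tests are run again, and significance may be declared from either classification. A reader who sees a significant p-value from one split would take it as a 5% finding, although there were two correlated chances to obtain it for each outcome.

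**Working it through.** The documents give no sample size, power or error rate for the DRD5 comparison, so there is no figure to reproduce first.

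**Inputs from Protocol section 13.1**
- Two-sided 0.05 per test, no adjustment.
- Arm B has 16 to 30 patients. Arm C has 6 evaluable and up to 12 enrolled. Pooled N runs from 16 + 6 = 22 to 30 + 12 = 42.
- Three outcomes × two classifications = 6 tests.

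**Assumptions (not in the documents)**
- Staining is log-normal with log SD 0.5 to 2, represented by one variable.
- The fixed cut is at the median. As a check, the positive share is also set to 7/15 = 0.47, from the 8 negative and 7 positive Arm A patients in the survival comparison, and to 0.30 and 0.70.
- The Z-score reference is the sample mean.

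**Step 1. What a Z-score split does.** Z = (x − m)/s with s > 0, so Z > 0 exactly when x > m. Whatever m is, the rule is a cut of x at m. An error e in x becomes e/s in Z. Ranks and relative error do not change.

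**Step 2. Overlap of the two splits.** Two cuts of one variable give nested groups. With positive shares p1 > p2, the correlation of the two labels is phi = √[p2(1 − p1) / (p1(1 − p2))]. The share p1 − p2 changes group. For a log-normal variable the share above its own mean is p2 = 1 − Φ(log SD/2). With p1 = 0.5, phi = √[p2/(1 − p2)].

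**Step 3. Error for one outcome.** P(at least one significant) = 1 − P(|Z1| < 1.96 and |Z2| < 1.96) for two standard normal statistics with correlation phi.

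| Log SD | Above mean (p2) | Change group | phi | P(at least one) |
|---|---|---|---|---|
| 0.5 | 0.401 | 0.099 | 0.82 | 0.077 |
| 1 | 0.309 | 0.191 | 0.67 | 0.085 |
| 1.5 | 0.227 | 0.273 | 0.54 | 0.090 |
| 2 | 0.159 | 0.341 | 0.43 | 0.093 |

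The bounds are 0.05 if the two splits coincide and 1 − 0.95² = 0.0975 if they were independent.

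The check used a positive share of 7/15 over log SD 0.5 to 2.5, and shares of 0.30 and 0.70 at log SD 1.5. It gave phi 0.38 to 0.89, 7 to 45% of patients changing group, and an error of 0.071 to 0.094. If the fixed cut happens to lie close to the mean, there is little inflation. With p1 = 0.309 and p2 = 0.30, phi = √[0.30 × 0.691/(0.309 × 0.70)] = 0.98 and the error is 0.059.

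**Step 4. Small samples.** Null simulation at N = 22 to 42 with the asymptotic log-rank test gave 0.08 to 0.13 for at least one significant split on PFS or OS. Single log-rank tests already rejected at about 0.05 to 0.08, so part of that is not due to the second split. With each test corrected to 5% size, the result was about 0.07 to 0.095, in line with step 3.

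**Step 5. All outcomes.** Over the six tests, the simulated chance of at least one false positive was 0.22 to 0.30, against 0.16 to 0.18 for the three fixed-cut tests alone. ORR was drawn independently of PFS and OS, and these figures include the small-sample inflation.

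**The case against.** The strongest reply is that this is a secondary biomarker correlation, that the lack of adjustment is openly declared, and that the SAP may mean the analysis is never run or is redefined elsewhere. All of that stands and limits the impact. It does not make the word independent correct, and in these two documents section 13.1 is the only specification of the analysis.

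Independent may have been meant loosely, as not relying on the fixed thresholds. That is a fair reading of intent. Even so, rescaling the same values does not answer the stated worry about precision.

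The size rests on assumptions. The documents give no distribution of DRD5 staining. Some Arm A patients had no detectable expression, which a log-normal does not represent. The fixed rule combines two percentages where the calculation uses one. Only the bounds of 5% and 9.75% for positively correlated tests do not depend on the assumed distribution.

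The text also invites some stronger readings that it does not support:
- A reader might infer that the cut is the sample mean, so that a patient's status depends on who else enrolled. This is the ordinary reading, but no reference is named. An external reference would remove that dependence, though the data would still be the same.
- A reader might infer that most patients will be labelled negative. That follows only from an assumed right skew, which the documents do not show.
- A reader might infer that agreement between the splits will be presented as replication. Nothing says how concordance will be reported.

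**Conclusion.** The point holds as a defect of wording and of specification. The plan credits the Z-score split with an independence that its own procedure rules out, leaves the reference and input undefined, and allows significance to be declared from either classification.

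For one outcome the false-positive chance is about 7 to 9.5% instead of 5%, with each test at true 5% size, log-normal staining, the fixed cut at the median, the sample mean as reference and N of 22 to 42. It is lower if the two cuts nearly coincide. A reader might take the 8 to 13% seen with the asymptotic log-rank test as the price of the second split. That overstates it, because a single such test already runs at about 5 to 8%. A full doubling to 10% is not reached either, because the tests are positively correlated.

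Nothing here touches the primary PFS-6 test. The correction matters only if the DRD5 analysis is carried out, and it is minor.

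**What to change.** In Protocol section 13.1, or in whatever document defines the analysis outside the SAP:
- Delete the words claiming independence.
- Make the pre-stated threshold (above 0.018% strong or above 1% total) the single classification on which significance is declared.
- Report the Z-score split as a sensitivity analysis of the same data, with no significance claim. State its reference mean and SD and which percentage is normalised.

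This returns each outcome to one test at a nominal 5%. It leaves the openly declared lack of adjustment across ORR, PFS and OS as it is.

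The cost is wording and one exploratory significance claim. No data, visits or sample size change. If the sponsor prefers to keep both splits as tests, 0.025 for each keeps the error per outcome at or below 1 − 0.975² = 0.0494, at some loss of power.

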13.2 Interim Analyses

For Arm A, a futility interim analysis will be conducted after 16 patients are enrolled. Since PFS-6 requires at least six months post-study initiation follow-up for subjects without progressive disease, the binary endpoint PFS rate at two months (PFS-2) will be used to determine whether the accrual should be suspended after sixteen patients have accrued. If out of the first 16 patients enrolled, only 7 or less patients are observed to be progression free during the first 2 months after treatment initiation, further accrual in this arm will be discontinued. Assuming exponential distribution, the null and alternative for the PFS6 are translated into 0.44 vs. 0.67 rates for the PFS2. Under these rates the chances of observing 7 or less progression free patients out of the first 16 are 0.6 under the null and 0.046 under the alternative.

For Arm B, D, and F, separately, a futility interim analysis will be conducted after 16 patients who are evaluable for efficacy are enrolled. Since PFS-6 requires at least six months post-study initiation follow-up for subjects without progressive disease, the binary endpoint PFS rate at two months (PFS-2) will be one criteria used to determine whether the accrual should be suspended after sixteen patients have accrued. If out of the first 16 patients who are evaluable for efficacy are enrolled, there is no objective response and only 7 or less patients are observed to be progression free during the first 2 months after treatment initiation, further accrual in this arm will be discontinued. Assuming exponential distribution, the null and alternative for the PFS6 are translated into 0.44 vs. 0.67 rates for the PFS2. Under these rates the chances of observing 7 or less progression free patients out of the first 16 are 0.6 under the null and 0.046 under the alternative.

No interim analyses will be conducted for Arm C or E.

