5.3 Treatment and Evaluation Cycles

At the beginning of each treatment cycle (i.e., every 3 weeks) patients will also have safety laboratory studies, physical examination, assessment of KPS, and complete the MDASI questionnaire. During discussion of the patient's progress, adverse events and concomitant medications will be collected by targeted questioning.

Patients who remain on study will have tumor response assessments performed at 8 weeks (± 7 days) after initiation of therapy and then every 8 weeks (± 7 days) thereafter.

In addition to reassessment scans, confirmatory scans should also be obtained not less than 4 weeks following initial documentation of objective response (OR). To be assigned a status of PR or CR, changes in tumor measurements must be confirmed by repeat assessments that should be performed no less than 4 weeks after the criteria for response are first met.

Patients are to return to the clinic every 3 weeks during the first 6 months on trial. If after 6 months, the patient and the investigator may agree to extend the interval for clinic visits to every 9 weeks (3 cycles). The laboratory assessments must still be performed every three weeks but may be done locally. Brain MRI or CT (for patients who cannot receive MRI scans) will be repeated every 8 weeks, with a 10-day window is allowed after the first 6 cycles.

Unscheduled visits: If a brain surgery or biopsy is scheduled during the active study or within 30 days from the end of treatment date, the investigator may obtain tumor tissue with patient's consent.

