11. MEASUREMENT OF EFFECT

After signing informed consent patients will undergo screening procedures including baseline radiologic imaging by contrast-enhanced CT scan or MRI within 14 days prior to initiating study drugs.

Patients who remain on study will have tumor assessments performed at 8 weeks (± 1 week) after initiation of therapy and then every 8 weeks (± 1 week) thereafter. In addition to reassessment scans, confirmatory scans should also be obtained not less than 4 weeks following initial documentation of objective response. To be assigned a status of PR or CR changes in tumor measurements must be confirmed by repeat assessments that should be performed no less than 4 weeks after the criteria for response are first met.

Efficacy will be assessed by the RANO response criteria as noted below. RANO-HGG and RANO-LGG will be used for each evaluation to assess contrast-enhancing lesions and T2/FLAIR hyper-intense lesions, respectively.

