11.3 Response/Progression Categories

The modified RANO Response Criteria to be used in this study are summarized below. If changes in the primary field lesions lead to assessment of progressive disease, this assessment must be confirmed at least 4 weeks later.

11.3.1 Complete response (CR). All of the following criteria must be met:

- a) Complete disappearance of all enhancing measurable and non-measurable disease sustained for at least 4 weeks. In the absence of a confirming scan at least 4 weeks later, this scan will be considered only stable disease.
- b) No new lesions.
- c) All measurable and non-measurable lesions must be assessed using the same techniques as baseline.
- d) Participants must be on no steroids or on physiologic replacement doses only.
- e) Stable or improved non-enhancing (T2/FLAIR) lesions.
- f) Stable or improved clinically, for clinical signs and symptoms present at baseline and recorded to be disease related.

Participants with non-measurable disease cannot have a complete response. The best response possible is stable disease.

11.3.2 Partial response (PR). All of the following criteria must be met:

- a) Greater than or equal to 50% decrease compared to baseline in the sum of products of perpendicular diameters of all measurable enhancing lesions sustained for at least 4 weeks. In the absence of a confirming scan at least 4 weeks later, this scan will be considered only stable disease.
- b) No progression of non-measurable disease.
- c) No new lesions.
- d) All measurable and non-measurable lesions must be assessed using the same techniques as baseline.
- e) The steroid dose at the time of the scan evaluation should be no greater than the dose at time of baseline scan.
- f) Stable or improved non-enhancing (T2/FLAIR) lesions on same or lower dose of corticosteroids compared to baseline scan.
- g) Stable or improved, for clinical signs and symptoms present at baseline and recorded to be disease related clinically.

Participants with non-measurable disease cannot have a partial response. The best response possible is stable disease.

11.3.3 Progressive disease (PD).

Any of the following criterion must be met:

- a) > 25% increase in sum of the products of perpendicular diameters of enhancing lesions (over best response or baseline if no decrease) on stable or increasing doses of corticosteroids.
- b) Any new enhancing measurable lesion.

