- c) Clear clinical deterioration not attributable to other causes apart from the tumor (e.g., seizures, medication side effects, complications of therapy, cerebrovascular events, infection, etc.). The definition of clinical deterioration is left to the discretion of the investigator but it is recommended that a decline in the Karnofsky Performance Score (KPS) from 100 or 90 to 70 or less, a decline in KPS of at least 20 from 80 or less, or a decline in KPS from any baseline to 50 or less, for at least 7 days, be considered neurologic deterioration, unless attributable to co-morbid events or changes in corticosteroid dose.
- d) Failure to return for evaluation due to death or deteriorating condition.

11.3.4 Minor Response (MR).

Apply to T2/FLAIR hyper-intense lesions only. All of the following criteria must be met:

- a) 25–50% reduction in perpendicular diameters of lesion
- b) No new lesions.
- c) The steroid dose at the time of the scan evaluation should be no greater than the dose at time of baseline scan.
- d) Stable or improved, for clinical signs and symptoms present at baseline and recorded to be disease related clinically.

11.3.5 Stable disease (SD).

All of the following criteria must be met:

- a) Does not qualify for CR, PR, or progression.
- b) All measurable and non-measurable sites must be assessed using the same techniques as baseline.
- c) Stable clinically.

11.3.6 Unknown response status.

Progressive disease has not been documented and one or more measurable or non-measurable lesions have not been assessed.

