The primary efficacy endpoint is PFS-6, defined as the proportion of subjects in the analysis population who remain progression-free for at least six months following initiation of study therapy. Response for the primary analysis will be determined by the investigator assessment, and a confirmation assessment is required per RANO. If patients discontinue protocol therapy at or before 6 months without tumor imaging performed, the patient will be treated in the primary endpoint analysis as a treatment failure. Adjustments will not be made for multiple comparisons.

Secondary efficacy endpoints include: (1) ORR defined as the proportion of subjects in the analysis population who have complete response (CR) or partial response (PR) using RANO criteria; (2) duration of response, defined as time from first RANO response to disease progression in subjects who achieve a PR or better; (3) progression-free survival (PFS), defined as the time from initiation of study therapy to the first documented disease progression according to RANO or death due to any cause, whichever occurs first; and (4) overall survival (OS).

Additional supportive analyses of duration of response and PFS will be conducted using RANO criteria, in which a confirmation assessment of disease progression must be obtained at least 4 weeks after the initial disease assessment indicating progressive disease.

Safety will be assessed by quantifying the toxicities and grades experienced by subjects who have received ONC201, including serious adverse events (SAEs). Other safety endpoints include laboratory safety assessments, KPS status, and vital signs.

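### The two-month futility count is not tied to the week-8 scan, so progression first seen on a late but in-window scan can count as progression-free

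*Protocol*

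**What the plan says.** Protocol 13.2 bases the futility look on PFS at two months in the first 16 patients. Accrual in Arm A ends if "only 7 or less patients are observed to be progression free during the first 2 months after treatment initiation". Arms B, D and F use the same count, but stop only if there is also no objective response. The section gives PFS-2 rates of 0.44 under the null and 0.67 under the alternative, with stopping probabilities of 0.6 and 0.046.

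Protocol 5.3 has "tumor response assessments performed at 8 weeks (± 7 days) after initiation of therapy", and Section 11 repeats the same window. Section 13.1 has PFS "defined as the time from initiation of study therapy to the first documented disease progression according to RANO or death due to any cause". Section 11.3 adds that, when changes in the primary field lesions indicate progression, "this assessment must be confirmed at least 4 weeks later".

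Neither document gives two months in days, names the week-8 scan as the PFS-2 assessment, or says how to classify a patient whose first scan falls after the two-month date. The SAP does not mention PFS-2 or the interim look.

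**The concern.** The two-month date lies inside the window of the scan that is meant to establish two-month status. Take a tumour that has progressed by day 55 without clinical signs. Scanned on day 58, it is documented within two months. Scanned on day 63, also within the protocol window, it is documented after two months, and on the literal text the patient was progression-free throughout.

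On that reading the error has one direction. A late scan can turn a failure into a success, never the reverse. The look exists to stop an inactive arm, and the threshold is a count out of 16, so one patient can move the total from 7 to 8. What depends on it is whether an arm that has reached 16 goes on towards 30 evaluable patients.

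**Working it through.** **1. The plan's own figures.** For X ~ Binomial(16, p), P(X ≤ 7) is 0.595 at p = 0.44 and 0.047 at p = 0.67. The stated 0.6 and 0.046 therefore follow from the stated rates.

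**2. The exponential translation (13.1 and 13.2).** PFS-2 = PFS-6^(2/6).
- Null: 0.10^(1/3) = 0.464, not 0.44, and P(X ≤ 7) = 0.517.
- Alternative: 0.30^(1/3) = 0.669, and P(X ≤ 7) = 0.047.

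**3. The dates.** The scan window is 56 ± 7, i.e. days 49 to 63. Two months is 2 × 30.44 = 60.9 days on average, and 59 to 62 days by calendar. With a day-61 cut, days 62 and 63 are in window but late.

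**4. If the week-8 scan decides.** S(d) = PFS-6^(d/182.6), at d = 56:
- Null: 0.494, and P(X ≤ 7) = 0.42.
- Alternative: 0.691, and P(X ≤ 7) = 0.031.

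**5. The literal rule, scan days even over 49 to 63 (assumption).** Let c be the share of late-scanned patients' progressions that are recognised clinically or by death before the cut (also an assumption). The probability of counting as progression-free is

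p = [Σ S(d) over days 49–61 + Σ {S(d) + (1 − c)(1 − S(d))} over days 62–63] / 15.

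Under the null the first sum is 6.505, and S(62) + S(63) = 0.910.

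| c | p | P(X ≤ 7) |
|---|---|---|
| 0 | (6.505 + 2)/15 = 0.567 | 0.21 |
| 0.5 | (6.505 + 0.910 + 0.5 × 1.090)/15 = 0.531 | 0.31 |
| 1 | (6.505 + 0.910)/15 = 0.494 | 0.42 |

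Under the alternative, P(X ≤ 7) is 0.011 at c = 0 and 0.031 at c = 1.

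**6. Scans clustered at day 56 (assumed SD 3 days).** About 3% fall after day 61. With c = 0 the null p is 0.509 and P(X ≤ 7) is about 0.375, against 0.42 if the scan decides.

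**7. Sensitivity to the cut.** With even scan days and c = 0, a day-60 cut gives 0.14 and a day-62 cut gives 0.31.

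Two separate shifts must not be credited to late scans. Correcting 0.44 to 0.464 takes the null stopping probability from about 0.6 to 0.52. Reading status at 8 weeks rather than two months takes it to 0.42. The late-scan effect is what lies below 0.42. None of these figures includes the no-response condition in Arms B, D and F.

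**The case against.** The protocol nowhere states that a patient first scanned on day 62 or 63 is a success. Section 13.2 speaks of patients observed to be progression-free. Someone without a scan by two months could be held not to have been so observed, which pushes towards stopping. The Study Calendar defines an 8-week evaluation cycle, so a sensible team might simply use the first evaluation scan. Progression also does not need a scan: "Clear clinical deterioration not attributable to other causes apart from the tumor" counts, as does death, and patients are examined every three weeks. The overhang is about two days of a 15-day window. Under the alternative, late scans reduce wrongful stopping, and the final PFS-6 test is unaffected.

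Most of this stands as a limit on size. The clinical route is why c matters, and the even spread with c = 0 is a worst case for a given cut. It does not remove the defect. Several readings are available and the text selects none, so two teams could reach different decisions from the same data. The reading that follows most directly from the PFS definition is the one that favours continuing.

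A reader might infer that the whole decision rests on one count of 16. That holds only for Arm A, which Section 8.3.3 describes as closed. Arms B, D and F also require no objective response before they stop.

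**Conclusion.** The point holds as an undefined landmark with a one-sided consequence on the literal reading. Its effect is modest. Under the 10% null and a day-61 cut, P(X ≤ 7) falls from 0.42 to between 0.21 and 0.31 if scan days are even and none to half of the late-scanned progressions are caught earlier. It falls only to about 0.375 if scans cluster at day 56. These results rest on exponential PFS, an assumed scan-day distribution and an assumed rate of clinical detection; the documents give no data on the last two.

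A reader might go further and conclude that the interim look is demonstrably biased, or that a few late scans will carry an inactive arm past the threshold. The documents do not support that. They do not show that any given share of patients is scanned late, and they do not say how such patients are classified. The practical reach is the looks in Arms B, D and F that are still to be done or reported.

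**What to change.** In 13.2, define a PFS-2 failure as death, or progression first documented, on or before the first scheduled (week-8) assessment, whatever its day in the window. State that progression needing four-week confirmation under 11.3 is dated, once confirmed, to the assessment that first showed it. Without this, a tumour first seen to progress on day 58 and confirmed on day 86 or later is still unclassified.

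Replace 0.44/0.6 and 0.67/0.046 with the 8-week values: PFS of about 0.49 and 0.69, and P(X ≤ 7) of about 0.42 under the 10% null and 0.03 under 30%. Say that these come before the no-response condition.

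The cost is a few sentences, with no new data or visits. There is a downside to state openly: 0.42 is less favourable than the quoted 0.6, and than the 0.52 that applies at exactly two months. With the threshold kept at 7, the rule stops an inactive arm less often than the protocol says. For any look already done, the report should say which definition was used and whether the other would have changed the decision.
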